7.1.4 Slit-lamp examination (SLE)

The Slit-lamp examination (SLE) must be performed before the instillation of any dilating or anesthetic eye drops or the fluorescein agent.

The patient will be seated at the slit-lamp while being examined. Grading of the eyelids, lashes, conjunctiva, cornea, lens, iris and anterior chamber will be done according to the following scales:

Eyelid - Meibomian glands

Evaluation of the central ten Meibomian gland openings in the mid-portion of the upper eyelid:

- 0 = None (none are plugged).
- 1 = Mild (1 to 2 glands are plugged).
- 2 = Moderate (3 to 4 glands are plugged).
- 3 = Severe (All glands are plugged).

Eyelid - Erythema

- 0 = None (normal).
- 1 = Mild (redness localized to a small region of the lid(s) margin OR skin).
- 2 = Moderate (redness of most or all lid margin OR skin).
- 3 = Severe (redness of most or all lid margin AND skin).
- 4 = Very severe (marked diffuse redness of both lid margin AND skin).

Eyelid - Edema

- 0 = None (normal).
- 1 = Mild (localized to a small region of the lid).
- 2 = Moderate (diffuse, most or all lid but not prominent/protruding).
- 3 = Severe (diffuse, most or all lid AND prominent/protruding).
- 4 = Very severe (diffuse AND prominent/protruding AND reversion of the lid).

Lashes

- 0 = Normal
- 1 = Abnormal (specify)

Conjunctiva – Erythema

- 0 = None (normal).
- 1 = Mild (a flush reddish color predominantly confined to the palpebral or bulbar conjunctiva).
- 2 = Moderate (more prominent red color of the palpebral or bulbar conjunctiva).
- 3 = Severe (definite redness of palpebral or bulbar conjunctiva).

Conjunctiva - Edema

- 0 = None (normal).
- 1 = Mild (slight localized swelling).
- 2 = Moderate (moderate/medium localized swelling or mild diffuse swelling).
- 3 = Severe (severe diffuse swelling).
- 4 = Very severe (very prominent/protruding diffuse swelling).

Lens

- 0 = No opacification (normal lens).
- 1 = Mild lens opacification.
- 2 = Moderate lens opacification.
- 3 = Severe lens opacification.
- N/A = Patient with artificial lens

Iris

- 0 = Normal
- 1 = Abnormal.

Anterior Chamber Inflammation (Slit beam = 0.3 mm wide, 1.0 mm long)

- 0 = None (no Tyndall effect).
 - 1 = Mild (Tyndall effect barely discernible).
 - 2 = Moderate (Tyndall beam in the anterior chamber is moderately intense).
 - 3 = Severe (Tyndall beam in the anterior chamber is severely intense).
- Corneal findings of interest on the SLE include the horizontal diameter of the cornea (measured in mm at the time of the SLE using a ruler).

Relevant findings of the SLE will be entered in the eCRF.

7.1.5 Tear Film Break-up Time (TFBUT)

Patients with a Tear Film Break-up Time TFBUT test ≤ 10 in the study eye (study eye) at the screening visit are eligible for enrollment.

TFBUT will be measured by determining the time to tear break-up. The TFBUT will be performed after instillation of 5 μ l of 2% preservative-free sodium fluorescein solution into the inferior conjunctival cul-de-sac of each eye. The patient will be instructed to blink several times to thoroughly mix the fluorescein with the tear film. In order to achieve maximum fluorescence, the examiner should wait approximately 30 seconds after instillation before evaluating TFBUT. With the aid of a slit lamp at 10X magnification using cobalt blue illumination, the examiner will monitor the integrity of the tear film, noting the time it takes to form lacunae (clear spaces in the tear film) from the time that the eye is opened after the last blink. This measurement will be performed within 10 seconds maximum. The TFBUT will be measured twice during the first minute after the instillation of the fluorescein. If the 2 readings differ by more than 2 seconds a third reading is taken.

The TFBUT value will be the average of the 2 or 3 measurements.

Relevant TFBUT findings will be entered in the eCRF.

7.1.6 Schirmer test I (without anesthesia)

Patients with a Schirmer test without anesthesia ≤ 10 mm/5 minutes in the worse eye (study eye) at the screening visit are eligible for enrollment.

This test will be performed to measure aqueous tear secretion prior to the instillation of any dilating or eye drops. Both eyes may be tested at the same time.

This test will be conducted in a dimly lit room. While the patient looks upwards, the lower lid will be drawn gently downwards and temporally. The rounded bent end of a sterile strip will be inserted into the lower conjunctival sac over the temporal one-third of the lower eyelid margin. The test should be done without touching directly the Schirmer test strip with the fingers to avoid contamination of skin oils. The patients will be instructed to close their eyes gently.

After 5 minutes have elapsed, the Schirmer test strip will be removed and the length of the tear absorption on the strip will be measured (millimeters/5 minutes).

The wetting distance at 5 minutes for each eye will be recorded in the eCRF.

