5.2 Inclusion criteria

To be enrolled in this study, patients must fulfill all these criteria:

1. Patients (male or female) must be ≥ 18 years of age.
2. Patients must be diagnosed with any type of dry eye (e.g. Meibomian Gland Dysfunction, Blepharitis, Keratoconjunctivitis sicca etc) at least 3 months before enrollment.
3. Patients must present dry eye pathology characterized by the following clinical features:
 - a. Corneal and/or conjunctival staining with fluorescein and lissamine green using National Eye Institute (NEI) grading system > 3
 - b. Mean Symptom Assessment in Dry Eye (SANDE) questionnaire ≥ 30
 - c. Schirmer test without anesthesia < 10 mm/5 minutes and/or tear film break-up time TFBUT < 10 seconds in the study eye
4. The same eye (study eye) must fulfill all the above criteria.
5. Patients must have BCDVA score of ≥ 0.1 decimal units in both eyes at the time of study enrollment.
6. Female patients must have negative pregnancy test if at childbirth potential
7. Only patients who satisfy all requirements for informed consent may be included in the study. Written Informed Consent must be obtained before the initiation of any study-specific procedures.
8. Patients must have the ability and willingness to comply with study procedures.

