Baseline Visit	Day 0	
The following procedures will be performed (the below order is not mandatory):
 
 ➤ Explanation to the patient of study aims, procedures and possible risks ➤ Informed consent signature ➤ Screening number allocation (as S001, S002, etc.) ➤ Demographic data ➤ Medical and surgical history/current medical conditions ➤ Prior/concomitant medications ➤ AE collection ➤ Ocular examination of both eyes: 
 1. Assessment by SANDE questionnaire 2. Assessment of best corrected distance visual acuity (BCDVA) 3. Slit-lamp examination (SLE) to assess the eyelid (Meibomian glands), eyelid (erythema), eyelid (edema), lashes, conjunctiva erythema, lens, iris, anterior chamber 4. External Ocular Examination 5. TFBUT 6. Schirmer test I (without anesthesia) 7. Ocular surface staining (NEI score - fluorescein and lissamine green) 8. InflammADry (MMP-9) ➤ Frequency of patient's own artificial tear use (to be reported in eCRF) ➤ Pregnancy test for female patients if childbirth potential. ➤ Patient eligibility: Inclusion/exclusion criteria evaluation ➤ Assignment of the study eye ➤ Randomization ➤ Study Drug Dispensation 
The Investigator will dispense to the patients their monthly box containing the study drug for the following 4 weeks together with an adequate number of adapters and pipettes After completing baseline evaluation patients will start the study treatment as per instructions and will self-administer at home the subsequent doses till the evening of Day 28 (± 2). Patients will return to the clinical site on Day28 (Week 4 Visit).
 
The patients will be instructed to enter time of self-administration, AE occurrence, and concomitant medication intake into the diary, and to return the refrigerated box on the Week 4 visit.

At home	Days 0-28 ± 2	
 ➤ Self-administration at home of the IMP, six times daily every 2 h for both eyes (diary) ➤ Recording any new or changes in concomitant medications (diary) ➤ Recording any unusual medical conditions - AE monitoring (diary) 
Data will be recorded by the patient in the patient's diary.

	Day	Procedures/Assessments

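### The Baseline and Week 8 lists in Protocol 6.1 show, and permit, fluorescein TFBUT before the Schirmer test, an order that 7.1.6 excludes; the likely cost is noise in a secondary endpoint

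*Protocol*

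**What the plan says.** **Timing rule.** Protocol 7.1.6 on the Schirmer test: "This test will be performed to measure aqueous tear secretion prior to the instillation of any dilating or eye drops". SAP 8.2.7 carries the same rule.

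**What TFBUT involves.** Protocol 7.1.5 has the examiner instil "preservative-free sodium fluorescein solution into the inferior conjunctival cul-de-sac of each eye", after which the patient blinks to mix it into the tear film.

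**Visit lists.** For both Baseline and Week 8, the ocular examination in Protocol 6.1 runs "5. TFBUT 6. Schirmer test I (without anesthesia"), with NEI staining as item 7 and the MMP-9 test as item 8. Each list is headed with the remark that "the below order is not mandatory". Neither list refers to 7.1.6.

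**Related rule.** Protocol 7.1.4 says the slit-lamp examination "must be performed before the instillation of any dilating or anesthetic eye drops or the fluorescein agent".

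**Where Schirmer is used.** Inclusion criterion 3c in Protocol 5.2 reads: "Schirmer test without anesthesia < 10 mm/5 minutes and/or tear film break-up time TFBUT < 10 seconds in the study eye". Change in Schirmer is a secondary endpoint (Protocol 9.1.2). SAP 9.2 tests the Week 8 change in wetting distance by ANCOVA in the FAS and PPS. The schedule has Schirmer at Baseline and Week 8 only, and SAP 8.2.7 does not impute it.

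**The concern.** Protocol 7.1.6 presents the Schirmer test as a measure of aqueous tear secretion, and fluid put into the eye just beforehand bears directly on that quantity. The protocol's own timing rule shows that its authors wanted to avoid this. The visit list is what staff are likely to work from. If they go down it as printed, fluorescein comes first at both visits and 7.1.6 is broken. If they use the stated freedom, the same patient may be tested one way at Baseline and the other way at Week 8.

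The endpoint is the difference between two single readings, with no intermediate visit to dilute an inconsistency. Neither document mentions recording the order or time of the tests, and test order is not among the listed reasons for exclusion from the per-protocol set. A departure could therefore go unnoticed.

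**Working it through.** The plan states no figure here, so the check compares the texts and then reasons about how an order effect would pass into the analysis.

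**1. Can one sequence satisfy every section?**

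| Sequence | 6.1 lists | 7.1.4 (slit lamp before fluorescein) | 7.1.6 (Schirmer before drops) |
|---|---|---|---|
| Slit lamp, Schirmer, TFBUT, staining | Allowed (order optional) | Met | Met |
| Slit lamp, TFBUT, Schirmer, staining | Allowed, and the order printed | Met | Not met |

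The first row satisfies everything, so the sections can be reconciled. The second row is what the lists print. The printed order does respect 7.1.4, because slit lamp is item 3 and TFBUT item 5. The mismatch is with 7.1.6 only.

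**2. Is fluorescein an eye drop under 7.1.6?** Section 7.1.4 names fluorescein; 7.1.6 speaks only of dilating or eye drops. A solution instilled into the cul-de-sac is naturally read as a drop, but this is an inference.

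**3. Effect on the change score.** Let *d* be the shift in wetting length when fluorescein goes first. Its size and sign are not in the documents; assume it is additive and the same for all patients. Let *B* = 1 if fluorescein came first at Baseline and *W* = 1 if it came first at Week 8; otherwise 0. Then

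observed change = true change + *d*(*W* − *B*)

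| Baseline | Week 8 | Shift in change |
|---|---|---|
| Schirmer first | Schirmer first | 0 |
| Fluorescein first | Fluorescein first | *d* − *d* = 0 |
| Schirmer first | Fluorescein first | +*d* |
| Fluorescein first | Schirmer first | −*d* |

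The change is disturbed only when the order differs between visits. A constant order, even the wrong one, leaves the change intact under this model, although both absolute values move by *d*.

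**4. Effect within an arm.** If fluorescein comes first in a share *p_B* of patients at Baseline and *p_W* at Week 8, the arm's mean change moves by *d*(*p_W* − *p_B*). This is zero unless practice drifts between the visits.

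**5. Effect on the arm comparison.** The difference between arms moves by *d* times the difference between arms in (*p_W* − *p_B*). Under randomization and the masking in Protocol 8.3, staff have no basis for choosing the order by arm, so its expected value is zero. The baseline covariate in the ANCOVA does not alter this, because any baseline shift is also balanced in expectation.

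**6. Effect on precision.** If the order is chosen independently at each visit with the same share *p*, and is unrelated to the true change, the variance of the change rises by 2*p*(1 − *p*)*d*². This is zero when *p* is 0 or 1, that is, when the order is fixed. No number can be put in: the documents give neither *d* nor *p*, nor a standard deviation for Schirmer change.

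**7. Effect on eligibility.**

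| TFBUT in study eye | Does Schirmer decide criterion 3c? |
|---|---|
| Below 10 seconds | No; 3c is already met |
| 10 seconds or more | Yes |

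Only patients in the second row can be misclassified on 3c by a distorted Schirmer value.

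**The case against.** The strongest reply is that nothing here is contradictory. The rule in 7.1.6 is specific and unconditional, and the SAP repeats it. The remark about order heads the whole visit list, including consent and randomization, while 6.1 separately requires consent before any study procedure. It is therefore a general checklist disclaimer that leaves the specific rules in force, and a site that reads section 7 will do Schirmer first. This stands as far as it goes: the documents do not conflict in the strict sense. It does not explain why the list prints the excluded order, without a cross-reference, at the only two visits where it matters.

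Three stronger readings are tempting and are not supported:

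- *A switch of order biases the treatment effect.* A reader might infer this from the shift *d* in individual change scores. An order unrelated to arm shifts both arms alike in expectation. Within-arm means can move; the comparison should not.
- *Ineligible patients are widely admitted.* Criterion 3c is joined by and/or, so Schirmer decides only when TFBUT does not qualify. If added fluid lengthens wetting (an assumption), the error would tend to exclude eligible patients rather than admit ineligible ones.
- *The lists also break 7.1.4.* They do not; the slit lamp is listed before TFBUT.

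It is also fair to say that the stakes are limited. Schirmer is one of several secondary endpoints, and the SAP describes all testing as exploratory and unadjusted for multiplicity.

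**Conclusion.** The point holds as an internal inconsistency worth correcting. The 6.1 lists display and permit an order that 7.1.6 excludes, and they allow it to differ between the only two Schirmer measurements. The expected consequence is avoidable noise in the Week 8 change in wetting distance, and a shift in within-arm mean change if practice drifts between visits. The primary SANDE endpoint, a questionnaire, is untouched.

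The size is unknown. The documents support no millimetre or power figure, and the loss is nil if the site keeps one order throughout.

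The conclusion rests on three assumptions: instilled fluorescein counts as an eye drop under 7.1.6; a preceding drop can alter wetting length, which the timing rule itself suggests; and the order does not depend on treatment arm, which randomization and masking make reasonable.

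**What to change.** Reconcile Protocol 6.1 with 7.1.6:

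- In the Baseline and Week 8 lists, put Schirmer ahead of the fluorescein-based tests (TFBUT and NEI staining), with the slit-lamp examination still before fluorescein as 7.1.4 requires.
- State that this order is mandatory and the same at both visits, and limit the remark about optional order to the other procedures.
- In 7.1.6, say that eye drops include fluorescein.

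The place of SANDE, BCDVA and the MMP-9 sample is for the sponsor to set; sections 7.1.4 and 7.1.6 do not determine it.

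The cost is a wording change in two lists and one section, with a matching change to any site worksheet. It adds no test, visit or patient burden and leaves the planned analysis as it is.

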7.1.7 Ocular surface staining (NEI score - Lissamine green and fluorescein)

As grading scale of the corneal and conjunctiva damage, the NEI/Industry Workshop guidelines will be used (10). The cornea is divided into five sectors (central, superior, inferior, nasal and temporal), each of which is scored on a scale of 0–3, with a maximal score of 15. Both nasally and temporally, the conjunctiva is divided into a superior paralimbal area, an inferior paralimbal area and a peripheral area with a grading scale of 0–3 and with a maximal score of 9 for the nasal and temporal conjunctiva.

For a better reading it is also essential not to use an intense illumination beam, which may reduce the contrast and lead to an underestimation of grading (5).

7.1.8 InflammDry:

InflammDry is a rapid, in-office test that detects MMP-9, an inflammatory marker that is consistently elevated in the tears of patients with dry eye disease. Using direct sampling microfiltration technology, InflammDry accurately identifies elevated levels of MMP-9 protein in tear fluid samples taken from the inside lining of the lower eyelid, the palpebral conjunctiva.

8 ASSIGNMENT OF STUDY TREATMENT

After obtaining informed consent a consecutive screening number will be assigned to each patient according to the sequence of study entry, from 001 to 150.

8.1 Randomization

Eligible patients will be randomized 2:1 to either rhNGF eye drops 20 µg/ml (100 patients) or vehicle solution (50 patients).

Each randomized patient will be allocated with randomization number to a consecutive list of starting with 1001 onwards.

Drop outs after randomization will not be replaced.

8.2 Treatment allocation

Each randomized patient will receive masked study treatment (either rhNGF eye drops 20 µg/ml or vehicle solution) according to the randomization code and determined by the allocated randomization number.

8.3 Masking

The identity of the treatments will remain unknown to the patient, Investigator, site staff and Sponsor's clinical research personnel until the study is unmasked for the final statistical analysis (after data base lock) except in case of specific events that will require unmasking of the patient.

The vials containing rhNGF (20 µg/ml) or vehicle will be identical in appearance, and the contents of the vials will be indistinguishable. All staff directly involved in the analysis of study results will remain masked to treatment assignments while the study is in progress.

A list of sequential kit numbers will be generated by a member of the CRO SAS programming group not involved in the conduct of the study. Each kit number will be randomly associated with a treatment group. Patients will be assigned to treatment in numerical order. A tear-off label from the kit box, with the kit number, will be attached to the investigational product dispensing log.

If the Investigator becomes unmasked for any reason, this information will be recorded on source data and in the eCRF of the study, specifying the date and the reason.

In the event of a medical emergency where the knowledge of patient treatment is required to provide the patient with appropriate care, Investigators will have the possibility to unmask the treatment assignment for a specific patient. . The Investigators are encouraged to contact the CRO staff before becoming unmasked if there is sufficient time.

9 EVALUATION PARAMETERS

9.1 Study variables

Clinical efficacy and safety parameters will be evaluated at each time point:

9.1.1 Primary endpoint

- Change from baseline in Symptom Assessment in Dry Eye (SANDE) scores for severity and frequency assessed at 8 weeks of treatment (with LOCF imputation at earlier end of trial assessment)

9.1.2 Secondary endpoints

- Change from baseline in SANDE scores for severity and frequency assessed at 4 and 8 weeks of treatment (without imputation)
- Changes in Cornea and conjunctival vital staining with fluorescein, National Eye Institute (NEI) scales
- Changes in Tear film break-up time (TFBUT) and Schirmer test I

9.1.3 Exploratory endpoint

- Changes in levels of the inflammatory biomarker matrix metalloproteinase 9 (MMP-9) in tears, measured by the RPS InflammDry detector

9.1.4 Safety endpoints

- Incidence and frequency of Treatment-emergent adverse events (TEAEs), assessed throughout the study

Analyses of endpoints will be performed based on evaluations obtained on days 0, 28±2, 56±4 and 28±4 days after discontinuation of study treatment. Details of analyses will be presented in the Statistical Analysis Plan finalized before Database Lock.

Details on the assessments are given in § 7.1.

10 STATISTICAL METHODS

The data documented in this study will be summarized using descriptive summary statistics, i.e., arithmetic mean, standard deviation (SD), (%), minimum, median, and maximum values for quantitative variables, and frequencies for qualitative variables.

A statistical analysis plan (SAP) will be developed and finalized before database lock and de-masking. Final statistical analysis on the study variables will be presented in detail in the SAP.

10.1 Analysis Sets

10.1.1 Definitions

A patient will be defined as screened after the signature of the informed consent, regardless of the completion of all the screening procedures.

A patient will be defined as eligible if he/she respects all the inclusion/exclusion criteria. Otherwise he/she will be defined as a screen failure.

A patient will be defined as enrolled in the study if he/she is randomized.

- Enrolled Set: all enrolled patients. This analysis set will be used for demographic, baseline and background characteristics
- Safety Set (SAF): all enrolled patients who receive at least one dose of the investigational medicinal product at the study eye. This analysis set will be used for the safety analysis
- Full Analysis Set (FAS): all patients in the FAS who have at least one post-baseline efficacy measurement. This analysis set will be used for the primary efficacy analysis
- Per Protocol Set (PP): all patients in the FAS who fulfil the study protocol requirements in terms of investigational medicinal product intake and collection of primary efficacy data and with no major deviations that may affect study results. This analysis set will be used for supportive efficacy analysis

Each patient will be coded by the CRO Biometry Unit as valid or not valid for the Enrolled Set, FAS, FAS and PP. Patients will be evaluated according to the treatment dose they will actually receive.

10.1.2 Reasons for exclusion from the Full Analysis Set

Reasons for the exclusion from the Full Analysis Set are the following:

- failure to take at least one dose of the IMP at the study eye
- lack of any efficacy data post enrollment

10.1.3 Reasons for exclusion from the Per Protocol set

Reasons for the exclusion from the Per Protocol set will be determined in the Blind Data Review Meeting and can be the following:

- lack of compliance with IMP administration (see § 10.3)
- exposure to an IMP dose different from the one assigned to the patient
- missing primary efficacy data
- failure to satisfy any inclusion/exclusion criteria (eligibility violations)
- intake of prohibited medications

